### 7.2. Participant Discontinuation/Withdrawal from the Study

Study staff should make every effort to encourage participants to remain in the study and to continue to use the Study App. A participant may withdraw from the study at any time at their own request or may be withdrawn at any time at the discretion of the investigator for safety, behavioral, or compliance reasons. This is expected to be uncommon.

A participant cannot withdraw consent for use of data already collected as part of the study. If the participant withdraws consent for disclosure of future information, the sponsor may retain and continue to use any data collected before such a withdrawal of consent.

Participants who prematurely discontinue study participation must complete the early termination procedures as described in the SoA (Section 1.2). Participants who discontinue use of the Study App prematurely should ideally be observed until the end of the study as if they were still using the Study App. The Study App on the discontinued participant's smartphone device will be disabled as described in Section 6.2. For all participants, the reason for discontinuation (e.g., AEs) must be recorded in the eCRF. These data will be included in the study database and reported.

Participants who are not actively using the Study App may be less motivated to adhere to the study visit schedule. Investigators and study staff should work to detect early signs of waning interest and encourage continued participation.

## 7.3. Lost to Follow-up

A participant will be considered lost to follow-up if he or she repeatedly fails to attend scheduled visits and is unable to be contacted by the study investigator or designee.

The following actions must be taken if a participant fails to attend a required study visit:

- The investigator or designee must attempt to contact the participant and reschedule the missed visit as soon as possible and counsel the participant on the importance of maintaining the assigned visit schedule and ascertain whether or not the participant wishes to and/or should continue in the study.
- Before a participant is deemed lost to follow up, the investigator or designee must make every effort to regain contact with the participant. Study staff will conduct a minimum of 3 communication attempts (via chat, SMS, email, or telephone). These contact attempts should be documented in the participant's record.
- Should the participant continue to be unreachable, he/she will be considered to have withdrawn from the study.

#### 8. STUDY ASSESSMENTS AND PROCEDURES

Study assessments and procedures, including their timing, are summarized in the SoA (Section 1.2). Adherence to the study design requirements, including those specified in the SoA, is essential and required for study conduct. Protocol waivers or exemptions are not allowed. Every effort should be made to ensure that the protocol required assessments and procedures are completed as described. All scales should be administered by individuals who have been appropriately trained. Study procedures are described in Section 4.1. Effectiveness and safety assessments are described below.

#### 8.1. Study Assessments

The following effectiveness assessment scales are used in this trial at the times as provided in the SoA (Section 1.2). A description of the scales and the respective scoring algorithms for all endpoints will be provided in the Statistical Analysis Plan (SAP).

#### 8.1.1. Migraine Patient Journey Questionnaire

The Migraine Patient Journey Questionnaire is a 4-item Click-generated self-report questionnaire to characterize migraine history.

#### 8.1.2. Monthly Migraine Days (MMD)

Participants will record the number of days per month (defined as 28 days) a participant experiences migraine events within the Study App.

#### 8.1.3. Identify Chronic Migraine (ID-CM)

The Identify Chronic Migraine (ID-CM) (Lipton, 2016) is a 12-item self-report standardized assessment designed to assess presence of self-report migraine diagnosis and subsequently categorizes respondents as meeting diagnostic criteria for either episodic or chronic migraine.

[figure not shown]
#### 8.1.4. Migraine-Specific Quality-of-Life (MSQ)

The Migraine-Specific Quality-of-Life Questionnaire version 2.1 (MSQ) (Rendas-Baum, 2013) is a 14-item questionnaire that measures the impact of migraine across three essential aspects of a patient's health-related quality of life over the past 4 weeks.

#### 8.1.5. Migraine Disability Assessment Scale (MIDAS)

The Migraine Disability Assessment (MIDAS) (Stewart, 1999) questionnaire is a brief, self-report 7-item questionnaire designed to quantify headache-related disability over a 3-month period.

| 8.1.6. |  |  |
|--------|--|--|
|        |  |  |

#### 8.1.10. Patient Global Impression of Change (PGI-C)

The Patient Global Impression of Change (PGI-C) is a self-reported, 7-point scale depicting a patient's rating of overall improvement. PGI-C has been validated in a number of other episodic diseases against well-established measures of pain intensity, pain interference in daily life, and treatment effectiveness. (Perrot, 2019)

## 8.2. Study App Engagement Assessments

## 8.3. Safety Assessments

## 8.4. Adverse Events (AEs), Serious Adverse Events (SAEs), and Other Safety Reporting

The definitions of adverse events (AEs) and serious adverse events (SAEs) can be found in Section 10.3.2.

The definitions of device-related safety events, (adverse device effects [ADEs] and serious adverse device effects [SADEs]), can be found in Section 10.7.1 and Section 10.7.2, respectively.

AEs will be reported by the participant (or, when appropriate, by a caregiver, surrogate, or the participant's legally authorized representative).

Clinical Study Protocol Amendment 3 CT-132-R-001

The investigator and any qualified designees are responsible for detecting, documenting, and recording events that meet the definition of an AE or SAE and remain responsible for following up all AEs.

The method of recording, evaluating, and assessing causality of AEs and SAEs and the procedures for completing and transmitting SAE reports are provided in Appendix 3.

#### 8.4.1. Time Period and Frequency for Collecting AE and SAE Information

All AEs and SAEs will be collected from the signing of the informed consent form (ICF) until the follow-up visit at the time points specified in the SoA (Section 1.2).

AEs will be divided into non-treatment-emergent AEs (non-TEAEs) and treatment-emergent AEs (TEAE). Non-TEAEs are those AEs that occurred prior to the first study treatment and TEAEs are those AEs with onset date/time at or after the first study treatment.

All SAEs will be recorded and reported to the sponsor or designee immediately and under no circumstance should this exceed 24 hours, as indicated in Appendix 3. The investigator will submit any updated SAE data to the sponsor within 24 hours of it being available.

Investigators are not obligated to actively seek information on AEs or SAEs after conclusion of the study participation. However, if the investigator learns of any SAE, including a death, at any time after a participant has been discharged from the study, and he/she considers the event to be reasonably related to the study intervention or study participation, the investigator must promptly notify the sponsor.

#### 8.4.2. Method of Detecting AEs and SAEs

Care will be taken not to introduce bias when detecting AEs and/or SAEs. Open-ended and non-leading verbal questioning of the participant is the preferred method to inquire about AE occurrences.

#### 8.4.3. Follow-up of AEs and SAEs

After the initial AE/SAE report, the investigator is required to proactively follow each participant at subsequent visits/contacts. All SAEs will be followed until resolution, stabilization, the event is otherwise explained, or the participant is lost to follow-up (as defined in Section 7.3). Further information on follow-up procedures is provided in Appendix 3.

#### 8.4.4. Regulatory Reporting Requirements for SAEs

Prompt notification by the investigator to the sponsor of an SAE is essential so that legal obligations and ethical responsibilities towards the safety of participants and the safety of a study intervention under clinical investigation are met.

The sponsor has a legal responsibility to notify both the local regulatory authority and other regulatory agencies about the safety of a study intervention under clinical investigation. The sponsor will comply with country-specific regulatory requirements relating to safety reporting to the regulatory authority, Institutional Review Boards (IRB)/Independent Ethics Committees (IEC), and investigators.

An investigator who receives an investigator safety report describing an SAE or other specific safety information (e.g., summary or listing of SAEs) from the sponsor will review and then file it along with other appropriate documentation (e.g., Investigator's Brochure) and will notify the IRB/IEC, if appropriate according to local requirements.

#### 8.4.5. Pregnancy

Pregnancy will not be excluded from participating in the study. However, because pregnancy is a major life event, the sponsor will track pregnancy status. Details of all pregnancies in female participants will be collected after the start of study intervention and until the end of Week 13.

If a pregnancy is reported, the investigator will record pregnancy information on the appropriate form and submit it to the sponsor within 24 hours of learning of the female participant pregnancy.

While pregnancy itself is not considered to be an AE or SAE, any pregnancy complication or elective termination of a pregnancy for medical reasons will be reported as an AE or SAE.

Abnormal pregnancy outcomes (e.g., spontaneous abortion, fetal death, stillbirth, congenital anomalies, ectopic pregnancy) are considered SAEs and will be reported as such.

Any female participant who becomes pregnant while participating in the study can continue in the study as planned. Prior to continuation of study intervention following pregnancy, the investigator must agree to monitor the outcome of the pregnancy and the status of the participant and her offspring.

#### **8.4.6.** Reporting of Investigational Device Complaints

An investigational device complaint (IDC) is any written, electronic, or oral communication by a HCP, consumer, participant, medical representative, regulatory agency, partner, or other third party that alleges Inadequacy of a medical device related to its identity, quality, durability, reliability, safety, or performance, such as malfunction, misuse or use error and inadequate labeling.

For this study, all IDCs related to the Study App are reportable to the sponsor.

#### **8.4.6.1.** Eliciting and Reporting Device Complaints

During the study, possible or suspected Study App IDCs will be gathered by Click via Click's technical support resource. Instructions for reporting IDCs can be found in the Study App Instructions.

#### 8.5. Pharmacokinetics

Not applicable.

### 8.6. Genetics and/or Pharmacogenomics

Not applicable.

#### 8.7. Biomarkers

Not applicable.

## 8.8. Immunogenicity Assessments

Not applicable.

## 8.9. Health Economics

Not applicable.

#### 9. STATISTICAL CONSIDERATIONS

#### 9.1. Statistical Hypotheses

The primary endpoint is the change from baseline in the number of MMD at Week 12. The null hypothesis for the primary endpoint is that there is no difference between the means of the treatment arms and the alternative hypothesis is that they are different.

An Analysis of Covariance (ANCOVA) model will be used to test this hypothesis, where the dependent variable is the change from baseline to Week 12 in MMD for each participant. A participant's baseline MMD will be the total number of migraine days recorded during the 28-day run-in period. The Week 12 MMD will be the total number of migraine days recorded over the previous 28 days (Weeks 9-12).

The model will adjust for the following covariates: treatment arm, baseline MMD, and baseline use of concomitant medications for prevention of migraine. Analysis will be conducted on the Intent-to-Treat (ITT) analysis set. Multiple imputations under Missing At Random will be used to account for early termination or missing daily reports. Further details will be described in the SAP.

The null hypothesis will be rejected in favor of the alternative hypothesis if the two-sided p-value is smaller than 0.05 and the result favors the CT-132 arm.

No adjustment for multiplicity is planned for the secondary endpoints.

#### 9.2. Sample Size Determination

Assuming a difference of 1.6 in the mean MMD between the two arms, and a common Standard Deviation (SD) of 5.8, 474 participants are required for the study (237 per arm) to ensure 85% power and using a two-sided alpha of 5%.

Sample size was calculated using a two-sample t-test assuming equal variance. Assuming 15% drop out, at least 558 participants will be randomized in a 1:1 ratio to CT-132 or Digital Control.

## 9.3. Analysis Sets

For the purposes of analysis, the following analysis sets are defined:

| Analysis Set          | Description  |
|-----------------------|--|
| Consented             | All participants who signed the ICF.   |
| Enrolled              | All participants who signed the ICF and completed the run-in period.   |
| Intent-To-Treat (ITT) | The ITT set includes all enrolled participants who were randomized, based on the assigned intervention in the randomization and recorded in the database, regardless of treatment by Study App intervention.  This will be the main analysis set for all effectiveness analysis. |

| Modified Intent-to-Treat (mITT) |  |
|---------------------------------|--|
| Per Protocol (PP)               |  |
| Safety                          | All randomized participants who were exposed to study intervention (completed at least one task). Participants will be analyzed according to the intervention they received. This analysis set will be used for all safety analyses. |

## 9.4. Statistical Analyses

The SAP will be finalized prior to database lock and it will include a more technical and detailed description of the statistical analyses described in this section. This section is a summary of the planned statistical analyses of the most important endpoints including primary and secondary endpoints.

#### 9.4.1. General Considerations

For continuous variables, summary tables will provide the number of observations [n], mean, standard deviation, median, minimum and maximum. For categorical variables, summary tables will provide the number of observations [n] and frequency of each category (including missing data). Tabulations will be presented by treatment and overall, when appropriate.

Modeling and testing will be described for each endpoint.

#### 9.4.2. Participant's Disposition

The number of participants who were screened and enrolled to the study will be presented, as well as the reason for not being randomized. The number of participants who discontinue the study will be presented by reason for discontinuation. The number of participants in the ITT, mITT, PP, and safety analysis set will be presented.

#### 9.4.3. Demographics and Baseline Characteristics

In order to assess the comparability of the two arms at baseline, demographic and baseline characteristics data will be summarized by treatment group. These summaries will be presented for the ITT set. If there is a difference of more than five participants in the total number of participants between the ITT and the safety, mITT and PP analysis sets, the summaries will be presented for these sets.

#### 9.4.4. Primary Endpoint

The primary analysis will include the ITT set.

The primary endpoint is change in the number of MMDs from baseline (28-day run-in period) to Week 12 (previous 28 days, Week 9 through Week 12). The primary endpoint will be analyzed using an ANCOVA model, where the dependent variable is the change from baseline to Week 12 in MMD for each participant. A participant's baseline MMD will be the total number of migraine days recorded during the 28-day run-in period. The Week 12 MMD will be the total number of migraine days recorded over the previous 28 days (Weeks 9-12).

The model will adjust for the following covariates: treatment arm, baseline MMD, and baseline use of concomitant medications for prevention of migraine. Multiple imputations under Missing At Random will be used to account for early termination or missing daily reports. Details of imputation will be described in the SAP.

[figure not shown]
Least Squares Means (LSMEANS) for the difference in the change from baseline between the two treatment arms will be presented as well as the associated 95% confidence interval and two-sided p-value to test the null hypothesis of no difference. The study will be considered successful if the two-sided p-value will be  $\leq 0.05$ .

#### 9.4.4.1. Sensitivity Analysis for Primary Endpoint

The primary analysis will be repeated for the mITT and PP analysis sets.

The SAP will define additional analyses to assess impact of missing data.

#### **9.4.4.2. Subgroups**

### 9.4.5. Secondary Endpoints

Analysis of secondary endpoints will include the ITT set.

- Proportion of participants that have at least 50% reduction from baseline (28-day run-in period) in the number of MMDs to Week 12 (previous 28 days, Week 9 through Week 12). The proportion of patients who have at least a 50% reduction in MMDs will be compared between the two treatment groups using the normal approximation for difference between two proportions, for each of the complete data sets. The results will be combined using Rubin's rule.
- Change from baseline (28-day run-in period) in the number of MMDs recorded over the previous 28 days at Week 4 and at Week 8 will be analyzed in the same manner as the primary endpoint.
- Change from baseline (28-day run-in period) in the mean number of MMDs over 12 weeks. The endpoint will be analyzed in the same manner as the primary endpoint.
- Change in the number of headaches with at least moderate severity from baseline (28-day run-in period) to Week 12 (previous 28 days, Week 9 through Week 12). An ANCOVA model will be used to analyze this endpoint.
- Change from baseline (28-day run-in period) in the Migraine-Specific Quality-of-Life Questionnaire v2.1 (MSQ) total score over the previous 28 days at Week 4, Week 8, and Week 12. An ANCOVA model will be used to analyze this endpoint.
- Change from baseline in the Migraine Disability Assessment (MIDAS) to Week 12. This endpoint will be analyzed using Wilcoxon rank-sum test.

- Change from baseline (28-day run-in) to Week 12 (previous 28 days, Week 9 through Week 12) in the number of migraines with use of an acute medication. An ANCOVA model will be used to analyze this endpoint.
- Change in the number of MHDs from baseline (28-day run-in period) to Week 12 (previous 28 days, Week 9 through Week 12). The endpoint will be analyzed in the same manner as the primary endpoint, using MHDs instead of MMDs.

The SAP will elaborate on the analysis of other endpoints, covariates and handling of missing data.

#### 9.4.6. Multiplicity Control

No multiplicity adjustment will be made to secondary endpoints, sensitivity analyses, and subgroups.

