8.1.2. Primary Hypotheses

The null hypothesis that will be examined for the primary effectiveness endpoint is that there is no difference in effectiveness between the CT-132 treatment arm and the control in regard to the change from baseline (28-day run-in period) to Week 12 (previous 28 days, Week 9 through Week 12) in MMDs:

H₀:
$$\mu$$
_CT132 = μ _DC
H₁: μ _CT132 \neq μ _DC

Where μ _CT132 is the mean change from baseline (28-day run-in period) to Week 12 (previous 28 days, Week 9 through Week 12) in MMDs for the CT-132 treatment arm and μ _DC is the mean change from baseline (28-day run-in period) to Week 12 (previous 28 days, week 9 through Week 12) in MMDs for the digital control arm.

The success criterion for the study is rejection of the null hypothesis as defined above with a two-sided 0.05 alpha level.

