8.6. Multiplicity Control

No multiplicity adjustment will be made to secondary endpoints, sensitivity analyses, and subgroups. *P*-value and confidence interval for secondary endpoints not controlled for multiplicity and exploratory endpoints will be nominal and will not be used for statistical inference.

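### A cheap improvement, not an error: a short fixed sequence behind the primary test would allow confirmatory secondary conclusions that the plan now rules out

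*Protocol*

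**What the plan says.** There is one primary hypothesis, and it takes the whole alpha. SAP 8.1.2 says: "The success criterion for the study is rejection of the null hypothesis as defined above with a two-sided 0.05 alpha level". Protocol 9.5 plans no interim analysis.

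On the secondary endpoints, Protocol 9.1 says "No adjustment for multiplicity is planned for the secondary endpoints", and the synopsis agrees. Protocol 9.4.6 widens this: "No multiplicity adjustment will be made to secondary endpoints, sensitivity analyses, and subgroups". These protocol sentences establish only that the secondaries are uncontrolled. The bar on inference comes from SAP 8.6, under which p-values and confidence intervals for "secondary endpoints not controlled for multiplicity and exploratory endpoints will be nominal and will not be used for statistical inference".

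SAP 8.5.1 to 8.5.11 define 11 secondary analyses. Five of them (8.5.1, 8.5.4, 8.5.5, 8.5.10 and 8.5.11) are repeated in the mITT set. Neither document shows an order, a gate or an alpha allocation for any of them. SAP 10.1 nevertheless puts between-group p-values in the tables wherever a statistical model is used.

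**The concern.** The synopsis calls this a pivotal trial. The responder rate, the 12-week mean and the quality-of-life score help a reader judge whether a difference in mean migraine days matters to patients. Under SAP 8.6 none of them can support a formal conclusion, whatever the data show.

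The reader will still be given 11 unordered p-values, with no prespecified means of telling a key result from a chance one. The trial could gain formal secondary conclusions, and the documents give no reason for forgoing them.

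**Working it through.** **1. The plan's own sample size.** Inputs from Protocol 9.2: "Assuming a difference of 1.6 in the mean MMD between the two arms, and a common Standard Deviation (SD) of 5.8"; 85% power; two-sided 0.05; two-sample t-test with equal variance; 15% dropout.

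- Normal approximation: n per arm = 2 × (1.960 + 1.036)² × (5.8/1.6)² ≈ 236.
- Exact t-test: 236.93, so 237 per arm and 474 in total, with power 85.0%.
- Dropout: 474/0.85 = 557.6, so 558.

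The stated figures are reproduced. They involve the primary test only.

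**2. Number of secondary analyses.** The protocol lists eight secondary bullets. MMD at Weeks 4 and 8 splits into two, and MSQ at Weeks 4, 8 and 12 into three: 1 + 2 + 1 + 1 + 3 + 1 + 1 + 1 = 11. This matches SAP 8.5.1 to 8.5.11.

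**3. Error rate of the plan as written.** Only the primary test can yield a claim, so the chance of a false confirmatory claim is at most 0.05.

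**4. Error rate if the nominal p-values were read as findings.** With 11 true nulls and independent tests, 1 − 0.95¹¹ = 0.431. The documents give no correlations, so equal correlation between test statistics was assumed and simulated (300,000 runs per value). The primary was given its planned effect where marked.

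| Assumed correlation | 0 | 0.3 | 0.5 | 0.7 | 0.9 |
|---|---|---|---|---|---|
| At least one of 11 null secondaries below 0.05 | 0.431 | 0.375 | 0.303 | 0.223 | 0.132 |
| Same, and the primary also succeeds (primary effect real) | 0.368 | 0.310 | 0.234 | 0.151 | 0.069 |
| Fixed sequence: false secondary claim (primary effect real) | 0.043 | 0.041 | 0.036 | 0.030 | 0.026 |
| Fixed sequence: any false claim, all 12 nulls true | 0.049 | 0.050 | 0.050 | 0.050 | 0.050 |
| Fixed sequence: primary and first five secondaries very large, other six null | 0.051 | 0.050 | 0.049 | 0.050 | 0.050 |

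**5. Why the sequence holds 5%.** A false claim requires rejecting the first true null in the order. That null is tested at 0.05, so the chance of any false claim is at most 0.05 under any correlation. The 0.051 is simulation error. The primary is tested first at its full 0.05, so its alpha, its 85% power, the 474 evaluable and the 558 randomized are unchanged.

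**6. What the sequence does not guarantee.** Each step needs the primary and every earlier step to succeed. The documents give no secondary effect sizes, so the marginal power of each secondary is an assumption. The ranges below run from correlation 0 to 0.9.

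| Assumed marginal power of each secondary | Primary and first secondary pass | Through the third | Through all 11 |
|---|---|---|---|
| 85% | 0.72 to 0.81 | 0.52 to 0.77 | 0.14 to 0.70 |
| 70% | 0.60 to 0.69 | 0.29 to 0.60 | 0.02 to 0.51 |
| 50% | 0.43 to 0.50 | 0.11 to 0.39 | 0.00 to 0.30 |

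At correlation 0 and 85%, 0.85² = 0.72 and 0.85⁴ = 0.52, which agrees. The steady fall is why a short list is better than all 11.

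**7. Readiness of the candidate endpoints.** SAP 8.5.1 and 8.5.4 use the primary's 100 imputed datasets, and 8.5.11 follows the primary method in 8.1.3. MSQ (8.5.6) uses observed data only. In 8.5.1, R is a percent change, yet the printed responder cut-off is R ≤ 50%. A reduction of half or more would be R ≤ −50%. The minus sign may have been lost when the text was read from PDF.

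**The case against.** The strongest reply is that this is a deliberate and consistent choice. The protocol and SAP agree, confirmatory error is already held at 5%, and no planned secondary claim is undermined. Effect estimates and confidence intervals will be tabulated and can inform clinical meaning without a gate. All of this stands, so the point is an improvement and not a defect.

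A reader might infer three stronger things that the documents do not support:

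- **That the trial carries a 43% false-positive risk.** SAP 8.6 forbids the reading that would produce it. Independence is also unrealistic: the responder endpoint dichotomises change in Week 12 MMDs, the 12-week mean includes Weeks 9-12, and SAP 6.2 makes baseline MMDs a subset of baseline MHDs.
- **That SAP 8.6 implies a controlled subset.** Its reference to secondaries that are not controlled could suggest that others are. The sentence before it says none is adjusted, so this is loose wording and not a hidden hierarchy.
- **That a positive responder result is likely and is being wasted.** No responder rates appear in either document, so no power for that test can be claimed.

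It is also fair to object that the order proposed below is a reviewer's preference, and that the change involves more than an edit. Protocol 10.1.1 requires IRB/IEC approval of amendments before changes to the study design are implemented. Both objections stand. Neither outweighs the gain, because an endpoint after a failed step would keep exactly the nominal status it has today.

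**Conclusion.** The concern holds as a cheap improvement. All 11 secondary analyses are nominal and barred from inference, while a prespecified fixed sequence after the single primary test would allow confirmatory secondary conclusions with no change to primary alpha, primary power or N. *Allow* is the right word: success at each step depends on the primary and on every step before it.

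The 5% bound on the sequence needs no assumption about correlation. The figures of about 43%, or roughly 13% to 37% at correlations of 0.9 to 0.3, apply only to a reading the SAP rules out. They assume all 11 nulls true and, for the range, equal correlation.

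**What to change.** Before unblinding and database lock, replace the multiplicity text in Protocol 9.4.6 and SAP 8.6, and conform Protocol 9.1 and the synopsis, along these lines:

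> If the primary null hypothesis is rejected in favour of CT-132, the following are tested in the ITT set in this order, each at two-sided 0.05, stopping at the first failure: (1) 50% MMD responders at Week 12 (SAP 8.5.1); (2) mean MMDs over 12 weeks (8.5.4); (3) MHDs at Week 12 (8.5.11). All other secondary p-values, and any after a failed step, are nominal.

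The endpoints and order are an example, and the sponsor should choose them. Sensitivity analyses, subgroups and the mITT repeats need no place in the sequence.

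Preconditions:

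- Confirm that the responder rule in SAP 8.5.1 reads R ≤ −50%.
- Add MSQ at Week 12 (8.5.6) only if its missing-data handling is aligned with the primary analysis.
- State the direction of the gate in the SAP. Protocol 9.1 requires a result in favour of CT-132, but SAP 8.1.2 and 8.1.3 do not.

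The cost is a minor protocol and SAP amendment, with whatever ethics review it needs, and a commitment to an order now. It needs no alpha from the primary and no extra participants.
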